FiO ₂	Fraction of Inspired Oxygen
FDA	Food and Drug Administration
GCP	Good Clinical Practice
HIPAA	Health Insurance Portability and Accountability Act
ICU	Intensive Care Unit
IPV	Intrapulmonary Percussive Ventilation
IRB	Institutional Review Board
LE	Lung Expansion
LPM	Liters Per Minute
MV	Mechanical Ventilation
O ₂	Oxygen
PPC	Postoperative Pulmonary Complication
SpO ₂	Oxygen Saturation
SOP	Standard Operating Procedure

Hill-Rom®	Evaluation of The MetaNeb® System to reduce atelectasis as assessed by chest x-ray		
	CBI	06 March 2017	Rev C CR-RR2016- 001

Protocol Synopsis

Product Name:	The MetaNeb® System
Protocol Number:	CR-RR2016-001
Protocol Title:	Evaluation of The MetaNeb® System to reduce atelectasis as assessed by chest x-ray
Objective(s):	To evaluate the impact of use of The MetaNeb® System in clearance of atelectasis, as demonstrated by improvement in chest x-rays
Endpoints:	
Efficacy:
 
Primary Endpoint:
 
 • Chest x-ray assessed by Kelly Atelectasis Score [1] (Appendix 1) – Day 2 (approximately 48 hours) compared to baseline 
Secondary Endpoint(s):
 
 • Chest x-ray assessed by Kelly Atelectasis Score at Day 1 (approximately 24 hours) and at Day 4 (approximately 96 hours, or at discharge if discharge occurs before Day 4), compared to baseline • Chest x-ray improvement using a comparative scale (comparing baseline, Day 1, Day 2 and Day 4/discharge) • Oxygenation index (SpO₂/FiO₂ ratio) • Patient reported level of dyspnea - assessed by Modified Borg Dyspnea Scale (Appendix 2) • Change in patient respiratory status - subjective physician assessment –Respiratory Status Evaluation (Appendix 3) 
Safety:
 
 • Device-related adverse effects (adverse device effects) will be collected and evaluated.
Study Design:	The study will be a non-randomized open label study, with all subjects receiving treatment with The MetaNeb® System
Study Conduct:	The study will be conducted at one (1) site in the US.

Hill-Rom®	Evaluation of The MetaNeb® System to reduce atelectasis as assessed by chest x-ray	Page 7 of 29		
	CBI	06 March 2017	Rev C	CR-RR2016- 001

Treatment of Subjects:	Subjects who qualify for enrollment in the study will receive therapy with The MetaNeb® System following the labeled instructions for the device. Details of the treatment including duration and frequency will be defined in treatment procedures.
Duration of Subject Participation:	Duration of treatment with The MetaNeb® System will be a minimum of 48 hours, or until the subject is discharged from the hospital (if discharge is earlier). Enrolled subjects will remain in the study through Day 4 or until the subject is discharged from the hospital, whichever occurs sooner.
Number of Subjects:	Up to approximately fifteen (15) subjects will be enrolled.
Study Population:	Post-surgical (thoracic, cardiac or abdominal surgery) non-mechanically ventilated patients with significant atelectasis, as documented by chest x-ray results.
Inclusion Criteria	
Patients who meet all of the following inclusion criteria and no exclusion criteria will be included in the study:
 
 • Post-surgical (thoracic, cardiac or abdominal surgery) • Age \geq 18 years • Significant atelectasis by chest x-ray • Patient meets indication for therapy intervention as defined by Recruitment and Airway Clearance Protocol (Respiratory Department Policy and Procedure) • Signed informed consent

Hill-Rom®	Evaluation of The MetaNeb® System to reduce atelectasis as assessed by chest x-ray	Page 8 of 29		
	CBI	06 March 2017	Rev C	CR-RR2016- 001

Exclusion Criteria:	
Patients who meet one or more of the following exclusion criteria will not be eligible for the study:
 
 • Cause of atelectasis suspected to be infectious or solid mass • Requirement for mechanical ventilation • Requirement for chronic supplemental oxygen • Hemodynamically unstable, as defined by need for vasopressor therapy • Anticipated need for mechanical ventilation or other poor clinical outcome, unrelated to atelectasis or secretion retention • Contraindication to MetaNeb® therapy (untreated tension pneumothorax) • Inability to perform MetaNeb® therapy using a mouthpiece • Anticipated hospital discharge within 24 hours
Methods:	
Post-surgical patients with significant atelectasis confirmed by chest x-ray who require intervention and provide informed consent will be enrolled in the study. After enrollment, patients will be treated with The MetaNeb® System per a defined treatment regimen and within the approved product labeling. Details regarding therapy with The MetaNeb® System will be recorded.
 
After collection of the baseline chest-ray, chest x-rays during the treatment period will be assessed starting with Day 1 (approximately 24 hours) after initiation of treatment with The MetaNeb® System. In the case multiple chest x-rays are performed on a single day, the one closest to 24 hours from the previous day's chest x-ray will be used for study purposes.
 
Chest x-ray files will be sent to designated readers who are blinded to subject protected health information and/or date and time of chest x-ray. Chest x-rays will be scored using the Kelly atelectasis score. Chest x-rays will also be assessed using a comparative scale to evaluate intra-patient changes over time.
 
Any device related adverse events which occur after study enrollment and initial MetaNeb® therapy will be recorded.

Hill-Rom®	Evaluation of The MetaNeb® System to reduce atelectasis as assessed by chest x-ray	Page 9 of 29
	CBI	06 March 2017

Subject Withdrawal:	
Subjects may withdraw consent to participate in the study at any time. The subject may also be withdrawn from the study according to investigator judgement regarding the continued health or safety of the subject or related to inability or unwillingness to perform study therapy or procedures.

Statistical Methods:	
Descriptive summary statistics will be provided for demographics, the primary and secondary endpoints. Continuous data will be summarized with N, mean, median, standard deviation, min, and max. Categorical data will be summarized with the number and percent of patients in each category.
 
Shift tables from baseline to Day 1, Day 2, and Day 4/discharge will be tabulated for the Kelly atelectasis score and the patient reported level of dyspnea (modified Borg dyspnea scale). Proportions of subjects with improvement in atelectasis at Day 1, Day 2 and Day 4/discharge will be presented with ninety-five percent (95%) confidence interval. Time to a Kelly score of 1 in both lungs will be summarized with a Kaplan-Meier curve, with estimate of the median time and a 95% confidence interval.
 
The oxygenation index will be summarized by calculating the mean and standard deviation at each time point, as well as for changes from baseline.
 
Incidence of device-related adverse events (adverse device effects) will be tabulated.

Hill-Rom®	Evaluation of The MetaNeb® System to reduce atelectasis as assessed by chest x-ray			Page 10 of 29
	CBI	06 March 2017	Rev C	CR-RR2016- 001

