3.1 Overview of Study Design

3.1.1 Design:

The study will be a non-randomized open label study. It is a pre-post study design with subjects serving as their own control. All subjects will receive treatment with The MetaNeb® System. The study will be conducted at one (1) site in the US.

The study will evaluate the impact of the therapy on chest x-ray scores and related clinical endpoints. Patients with evidence of significant atelectasis on chest x-ray will be enrolled. After assessing baseline status, therapy with The MetaNeb® System will be introduced and incorporated into the respiratory care treatment regimen. Outcomes will be assessed at regular intervals following the initiation of the therapy.

3.1.2 Procedure:

Up to approximately fifteen (15) patients will be recruited and enrolled from the ICU and/or general care floors. Eligible subjects will be patients who are not intubated, and who have developed clinically significant atelectasis (i.e. described in the radiologist report). Demographic data will be collected from the medical record of each subject at the time of enrollment.

Following enrollment in the study, subjects will receive treatment with The MetaNeb® System per a defined treatment regimen and within the approved product labeling. Treatments will be delivered on a defined schedule. Enrolled subjects will be treated for a minimum of 48 hours, or until discharge (if discharge from the hospital occurs before 48 hours).

Chest x-ray files at baseline (Day 0), for enrolled subjects, will be collected. Daily chest x-ray files for Day 1 (approximately 24 hours), Day 2 (approximately 48 hours) and Day 4 (approximately 96 hours) or discharge (if discharge occurs before Day 4) will be collected as they become available.

All chest x-rays will be logged by subject number, date and time, and event (i.e. Day 0, Day 1 and Day 2, Day 4/discharge) and assigned a number from a random number list. All chest x-rays, identified only by the assigned number will be placed in a file for review and scoring by the blinded radiologist(s).

Pulse Oximetry SpO₂ data along with the subject's oxygen support status (O₂ delivered in LPM or %) from the time corresponding to the baseline and the Day 4/discharge

Hill-Rom®	Evaluation of The MetaNeb® System to reduce atelectasis as assessed by chest x-ray		
	CBI	06 March 2017	Rev C

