3.3 Evaluation Criteria/Effectiveness

The therapy regimen (treatment with The MetaNeb® System) will be evaluated to determine if there is an improvement in chest x-ray scores after initiation of the therapy. The study will also evaluate if there is a corresponding improvement in the clinical respiratory status of the patients demonstrated by a decrease in the O₂ requirement and/or an improvement in oxygen saturation. Endpoints are described below:

Primary Endpoint:

Chest x-ray score improvement at Day 2 (approximately 48) hours after initiation of therapy with The MetaNeb® System.

Chest x-rays will be scored using the Kelly scoring system (Appendix 1) to assess the presence of atelectasis on Day 2, after initiation of therapy with The MetaNeb®

Hill-Rom®	Evaluation of The MetaNeb® System to reduce atelectasis as assessed by chest x-ray			Page 15 of 29
	CBI	06 March 2017	Rev C	CR-RR2016- 001

System. Scores for chest x-rays at Day 2 will be compared to the scores for chest x-rays taken at baseline. The Kelly score for each of the chest x-rays will be assessed by blinded reader.

The baseline chest x-ray for each subject is the qualifying x-ray that determined the presence of significant atelectasis.

Secondary Endpoint(s):

- Chest x-ray score improvement at Day 1 (approximately 24 hours) and at Day 4 (approximately 96 hours or at discharge, if discharge occurs before Day 4) after initiation of therapy with The MetaNeb® System.

Scored using the Kelly score, as described above, to assess the presence of atelectasis.

- Chest x-ray improvement using a comparative scale after a minimum of forty-eight (48) hours of therapy with The MetaNeb® System.

Chest x-ray improvement assessed using a comparative scale for baseline, Day 1, Day 2 and Day 4/discharge. Four chest x-rays for each enrolled subject (baseline, Day 1, Day 2 and Day 4/discharge), with date and time masked, will be sent to the radiologist for comparison. The radiologist will rank the four x-rays 1, 2, 3 or 4 (1 = least atelectasis, 4 = most atelectasis).

- Oxygenation index ($\text{SpO}_2/\text{FiO}_2$ ratio) at Day 1, Day 2 and Day 4/discharge compared to baseline
- Patient reported level of dyspnea (assessed by Modified Borg Dyspnea Scale – Appendix 2)
- Change in patient respiratory status (Respiratory Status Evaluation – Appendix 3)

Physician observation and evaluation of patient respiratory status at time of enrollment (baseline) and on Day 2

Safety:

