3.4 Study Observations Table

The study observations and documentation timeline is outlined in Table 1.

Hill-Rom®	Evaluation of The MetaNeb® System to reduce atelectasis as assessed by chest x-ray		
	CBI	06 March 2017	Rev C

Table 1. Study Observations

Day	Day 0 (Treatment Initiation)	Day 1 (Post Treatment Initiation)	Day 2 (Post Treatment Initiation)	Day 4 / Discharge (or Early Termination)
Selection Criteria / Enrollment	X			
Informed Consent	X			
Demographic Data	X			
Medical History	X			
Chest X-ray Score (Kelly)	X (Baseline)	X	X	X
Chest X-ray Ranking (Comparative)				X
O2 Requirement Collected at time of Baseline and Day 4 / Discharge Chest X-rays.				
Collected at beginning of each shift for Day 1 and Day 2	X	X	X	X
SpO ₂ Collected at time of Baseline and Day 4 / Discharge Chest X-rays.				
Collected at beginning of each shift for Day 1 and Day 2	X	X	X	X
Borg Dyspnea Scale	X	X	X	
Respiratory Status Evaluation	X		X	
MetaNeb Treatments	X	X	X	X
Study Exit Form				X

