SpO₂/FiO₂ Ratio: The SpO₂/FiO₂ ratio (based on pulse oximetry readings and the O₂ requirement) for each subject will be calculated for the time of each chest x-ray. The SpO₂/FiO₂ ratio will also be calculated for the beginning of each shift for Day 0 – Day 2, or until the time of discharge from the hospital (if earlier).

Assessment of Dyspnea (Modified Borg Dyspnea Scale): An evaluation of each subject's dyspnea level will be assessed using patient response and a Modified Borg Dyspnea Scale. Evaluation will be completed by respiratory staff at the time of enrollment into the study (Day 0), and on a daily basis for Day 1 and Day 2, or at the time of discharge from the hospital (if earlier).

Respiratory Status Evaluation: An evaluation of each subject's respiratory status will be completed by the physician investigator at the time of enrollment into the study (Day 0) and on Day 2, or at the time of discharge from the hospital (if earlier).

MetaNeb® Treatments: All MetaNeb® treatments will be documented for each day beginning with enrollment (Day 0), Day 1 and Day 2, and through Day 4 or until the time of discharge from the hospital (if earlier).

Hill-Rom®	Evaluation of The MetaNeb® System to reduce atelectasis as assessed by chest x-ray		Page 18 of 29
	CBI	06 March 2017	Rev C

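### The rule for choosing among several films on one day counts from the previous day's film, not from treatment start, so it can pass over an available 48-hour film for the primary endpoint

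*Combined protocol and SAP*

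**What the plan says.** The time points are defined from the start of therapy. The Synopsis (Methods) says that films "will be assessed starting with Day 1 (approximately 24 hours) after initiation of treatment" with the device. Section 3.3 gives the primary endpoint as "Chest x-ray score improvement at Day 2 (approximately 48) hours after initiation of therapy". Table 1 in Section 3.4 heads the Day 1 and Day 2 columns as times after treatment initiation.

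The only rule for a day with several films stands in the Synopsis (Methods) and uses another origin: "In the case multiple chest x-rays are performed on a single day, the one closest to 24 hours from the previous" day's film is the one used for the study.

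The first film in that chain is the baseline film. Section 3.3 states: "The baseline chest x-ray for each subject is the qualifying x-ray that determined the presence of significant atelectasis". Consent, enrolment and first treatment all follow it. Table 1 places it in the column headed "Day 0 (Treatment Initiation", but no limit in hours is set on the gap between that film and the first treatment.

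Section 3.1.2 collects "Daily chest x-ray files for Day 1 (approximately 24 hours), Day 2 (approximately 48 hours) and Day 4 (approximately 96 hours", or discharge if earlier), as films become available. No Day 3 film is scheduled. Sections 3.1.2, 3.3, 3.4.1 and 3.5 give no tolerance around these times and no other selection rule.

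**The concern.** The endpoint and the selection rule use different time origins. The endpoint asks for the state of the lungs after about 48 hours of therapy. The rule asks for the film about one day after the last selected film. Any departure of the Day 1 film from 24 hours is carried in full into the Day 2 target, and on Day 1 itself the target is set by a film taken before treatment.

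The selected film feeds the Day 2 shift table, the proportion improved with its 95% confidence interval, and the within-subject ranking, which uses one film per time point. Hours of therapy at the primary film can then differ between subjects because of the rule itself, even when a film at the intended time exists. Section 3.5.1 says the study is meant to inform effect size and variability for later studies, so avoidable spread in exposure time matters to its stated use.

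The rule also fits Day 4 poorly. The previous day's film would be a Day 3 film, which the study does not schedule. A routine Day 3 film could serve if one happened to be taken.

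**Working it through.** **Inputs.** From the documents: the selection rule (Synopsis, Methods), targets of about 24 and 48 hours from treatment start (Synopsis and Section 3.3), and a baseline film that precedes treatment (Section 3.3). The plan gives no figure to reproduce. All film times below are assumptions, in hours from first treatment.

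**Formula.** Let *t*prev be the time of the previous day's selected film. The rule picks the film that minimises |*t* − (*t*prev + 24)|. For Day 2 the endpoint calls for the film that minimises |*t* − 48|. The two targets agree only when *t*prev = 24.

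**Switch points.** Suppose Day 2 has one film at 48 h and one *d* hours earlier. The midpoint is 48 − *d*/2, so the earlier film is chosen when *t*prev + 24 < 48 − *d*/2, that is, when *t*prev < 24 − *d*/2. By the same argument, with films at 48 and 48 + *d*, the later one is chosen when *t*prev > 24 + *d*/2.

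| *d* (h) | Earlier film chosen if Day 1 film is before | Later film chosen if Day 1 film is after |
|---|---|---|
| 6 | 21 h | 27 h |
| 12 | 18 h | 30 h |

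A search on a 0.25 h grid agrees: the last early switch and first late switch are 20.75 and 27.25 h for *d* = 6, and 17.75 and 30.25 h for *d* = 12.

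**Offset that starts at baseline.** Let the qualifying film be *L* hours before first treatment, with films at 24 − *L* and 24 h on Day 1, and at 48 − *L* and 48 h on Day 2. The Day 1 target is −*L* + 24, so the film at 24 − *L* is taken. The Day 2 target is then 48 − *L*.

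| *L* (h) | Day 1 / Day 2 film under the rule | Anchored at treatment start | Day 2 time as share of 48 h |
|---|---|---|---|
| 3 | 21 / 45 h | 24 / 48 h | 94% |
| 6 | 18 / 42 h | 24 / 48 h | 88% |
| 12 | 12 / 36 h | 24 / 48 h | 75% |

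The Day 2 choice is the same if the film at 24 − *L* is the only Day 1 film, so several films on Day 2 alone are enough. The 12 h row needs a film at 12 h to count as Day 1; the documents do not define a day.

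**Other direction, and no effect.** A sole Day 1 film at 30 h with Day 2 films at 48 and 54 h gives a target of 54 h, and the 54 h film is taken. A sole Day 1 film at 24 h gives a target of 48 h, so the 48 h film is taken whatever *L* is.

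**Illustrative size.** Assume two films on every day, uniform over 12–36 h and 36–60 h, and a baseline film at a uniformly distributed time before treatment, with the maximum gap set at 4, 8, 12 or 24 h. The two anchors then choose different Day 2 films in about 27% to 32% of subjects. Mean distance from 48 h is 4.9 to 5.2 h under the rule and 4.0 h when anchored at treatment start. Under a tighter assumption (a sole Day 1 film uniform over 20–28 h, two Day 2 films uniform over 44–52 h) the mean distances are 1.75 and 1.33 h. None of these spreads comes from the documents.

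**The case against.** The strongest reply is that the consequence is small. The rule is a tie-break within a day and can choose only among films already belonging to that day. The endpoint is set at approximately 48 hours with no tolerance, and films at 42, 45 or 54 h may fairly be called approximate. Even with generous assumptions the mean gain from re-anchoring is about 1 h (4.9 to 5.2 against 4.0), and about 0.4 h in the tighter case (1.75 against 1.33). Collecting films as they become available probably contributes more spread than the rule does. The rule is prespecified and does not depend on outcome, readers are blinded to date and time, and the study is a descriptive convenience sample with no test or threshold. Keeping films about 24 hours apart is itself an objective convention.

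Most of this stands as a limit on size. No bias in either direction is shown, and the effect on the Kelly score cannot be estimated because the documents give no rate of change over time. It does not justify the rule. Even if a 42-hour film is acceptable, the rule prefers it to a film at the stated target. No endpoint is an interval between successive films; the primary comparison is Day 2 against baseline. Blinding does not help either, because the rule decides which film is read.

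It is also fair to say that the case report form is not among the documents, so the clock time of first treatment may already be captured.

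**Conclusion.** The concern holds. On a day with several films, the stated rule can select a Day 2 film further from 48 hours of therapy than another film that is available. The mismatch equals the departure of the Day 1 film from 24 hours, and the switch points 24 − *d*/2 and 24 + *d*/2 follow from the rule. The particular film times are assumed.

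The effect is confined to days with several films, and it vanishes for Day 2 when the Day 1 film is at 24 hours. Its frequency and direction cannot be determined from the documents. If one subject of 15 changed category, the proportion improved would move by 1/15, about 7 percentage points, and by more if subjects are removed under the baseline Kelly exclusion in Section 3.5.1. This is a modest defect in a stated rule. It does not threaten the study, but it should be corrected because the correction is cheap.

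**What to change.** Replace the sentence in the Synopsis (Methods) with: *If several films are available, use the one closest to 24, 48 or 96 hours after the first MetaNeb treatment (or the discharge film where that provision applies).* This also removes the dependence of Day 4 on an unscheduled Day 3 film. Keep the qualifying film as baseline.

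Record the clock time of the first treatment. For each subject, list the hours from baseline film to first treatment and from first treatment to each selected film, so that readers can see the actual exposure behind each score.

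The cost is one sentence, one recorded time and one listing. Section 3.1.2 already provides that "All chest x-rays will be logged by subject number, date and time, and event". Section 3.4.1 says only that "treatments will be documented for each day beginning with enrollment (Day 0), Day 1 and Day 2" and onward, so the clock time of the first treatment should be required explicitly; this does no harm if the form already captures it. No new films or procedures are needed.

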3.2 Study Population

The study population consists of adult post-surgical (thoracic, cardiac or abdominal surgery) non-mechanically ventilated patients with evidence of significant atelectasis on chest x-ray, with an increasing need for respiratory support.

Hill-Rom®	Evaluation of The MetaNeb® System to reduce atelectasis as assessed by chest x-ray			Page 14 of 29
	CBI	06 March 2017	Rev C	CR-RR2016- 001

3.2.1 Inclusion Criteria:

Patients who meet all of the following criteria will be included in the study:

- Age \geq 18 years
- Significant atelectasis by chest x-ray
- Patient meets indications for therapy as defined by Recruitment and Airway Clearance Protocol (HOAG2013-0000002335/Version 4/Effective Date: 9/15/14)
- Signed informed consent

3.2.2 Exclusion Criteria:

Patients who meet any of the following criteria will be excluded from the study:

- Cause of atelectasis suspected to be infectious or solid mass
- Requirement for mechanical ventilation
- Requirement for chronic supplemental oxygen
- Hemodynamically unstable, as defined by need for vasopressor therapy
- Anticipated need for mechanical ventilation, or other poor clinical outcome, unrelated to atelectasis or secretion retention
- Contraindication to MetaNeb® therapy (untreated tension pneumothorax)
- Inability to perform MetaNeb® therapy using a mouthpiece
- Anticipated hospital discharge within 24 hours

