- Physician observation and evaluation of patient respiratory status at time of enrollment (baseline) and on Day 2 (Respiratory Status Evaluation – Appendix 3)

Safety:

Incidence of device-related adverse events (adverse device effects) will be tabulated.

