5.2 Complaints and Adverse Events Reporting

Hill-Rom®	Evaluation of The MetaNeb® System to reduce atelectasis as assessed by chest x-ray	Page 20 of 29
CBI	06 March 2017	Rev C

During the study, any adverse device effect, device-related complaint or allegation of injury (of any type) must be reported to the Sponsor within 24 hours. Please contact [name] by [contact] (office) PI [REDACTED] or email: [contact].

A complaint is defined as any written, electronic or verbal communication that alleges deficiencies related to the identity, design, quality, durability, reliability, safety, effectiveness or performance of the device. A serious injury is defined as an injury or illness that is life-threatening; results in permanent impairment of a body function or permanent damage to a body structure; or necessitates medical or surgical intervention to preclude permanent impairment of a body function or permanent damage to a body structure.

Any device complaint and/or allegation of injury shall be reviewed, evaluated, and investigated by Hill-Rom Post Market Surveillance and reported to the appropriate Health Authority per current regulations. The Investigators are responsible for informing the Institutional Review Boards, as per their guidelines.

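### Only events judged device-related count as safety data, so mechanical ventilation, new pneumothorax or death judged unrelated would not appear in the safety table

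*Combined protocol and SAP*

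**What the plan says.** Every statement about safety data is restricted by relatedness.

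- **Recording** (synopsis, Methods): "Any device related adverse events which occur after study enrollment and initial MetaNeb® therapy will be recorded".
- **Endpoint** (synopsis, Endpoints; repeated in 3.3, Safety): "Device-related adverse effects (adverse device effects) will be collected and evaluated".
- **Analysis** (synopsis, Statistical Methods; repeated in 3.5.2, Safety): "Incidence of device-related adverse events (adverse device effects) will be tabulated".
- **Reporting to the sponsor** (5.2): "During the study, any adverse device effect, device-related complaint or allegation of injury (of any type) must be reported to the Sponsor within 24 hours". What follows is also limited to what was reported: "Any device complaint and/or allegation of injury shall be reviewed, evaluated, and investigated by Hill-Rom Post Market Surveillance".
- **Serious events** (6.1): immediate reporting applies to serious and to unanticipated adverse device effects. There is no all-cause counterpart.

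Table 1 (3.4) has no adverse-event row. The one mention of adverse events of any cause, in 6.1, is a duty to provide medical care, not to record the event. No section says who judges relatedness or by what criteria.

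On the population, the narrative in 3.2 describes patients "with an increasing need for respiratory support". An exclusion in 3.2.2 reads "Anticipated need for mechanical ventilation, or other poor clinical outcome, unrelated to atelectasis or secretion retention".

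**The concern.** Relatedness decides whether an event enters the safety data at all. It is not an attribute noted on events that are all recorded. That matters more here than in a controlled trial. Everyone is treated, treatment is known, and no comparator arm would show an excess of events that had been put down to the underlying illness.

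Deterioration is also foreseeable. Sections 1.1 and 1.3 present atelectasis as leading to further pulmonary complications, and the exclusion on anticipated ventilation applies only where the cause is something other than atelectasis or retained secretions. In such patients, worsening can readily be attributed to the condition that brought them into the study.

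At stake is how the safety result reads. A report of no device effects could be accurate as labelled and yet say nothing about how many treated subjects were ventilated, had a new pneumothorax or died. Section 3.5.1 says the data may help plan later studies, whose designers would want those counts.

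**Working it through.** The plan states no safety rate, precision or power, and 3.5.1 calls the sample one of convenience. There is therefore no figure of the plan's own to reproduce. The check is a reading of the text, followed by an illustration of size.

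**1. Trace one event.** Suppose a subject starts mechanical ventilation on Day 1 and this is judged to come from the underlying disease.

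| Route | Where | Would it reach the safety table? |
|---|---|---|
| Safety recording | Synopsis, Methods | No: not device-related |
| Safety tabulation | 3.5.2 | No: same limit |
| Serious-event reporting | 6.1 | No: device effects only |
| Complaint or alleged injury | 5.2 | Only the sponsor's complaint process, and only if someone alleges it |
| Oxygen requirement and SpO₂ | Table 1, 3.4.1 | No: efficacy summary |
| Treatment exceptions | 3.1.4 | No: collected, with no stated analysis |
| Treatment log, exit form | Table 1, 3.4.1, 9.0 | No: no stated safety analysis |
| Respiratory Status Evaluation | 3.4.1, Appendix 3 | No: efficacy, and due only on Day 2 or at earlier discharge |

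A new pneumothorax fares the same way. The study readings of the films (3.3, Appendix 1) score or rank atelectasis, so a pneumothorax would be found only in the routine radiology report. A death judged unrelated also has no place in the safety tabulation.

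The efficacy tables need not reveal the loss either. Section 3.5.2 explains falling numbers by improvement and stopping the device, and carries the last score forward. It does not mention loss through deterioration.

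**2. Illustrate the size.** The inputs are n = 15 (synopsis; 3.1.2) and two assumptions that the documents do not supply. These are r, the any-cause risk per subject of such an event, and q, the chance that an event is called device-related. Subjects are taken as independent, with at most one event each.

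- P(table empty) = (1 − rq)^15
- P(no event at all) = (1 − r)^15
- P(at least one event, table empty) = (1 − rq)^15 − (1 − r)^15

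For r = 10% and q = 25%: 0.975^15 = 0.684 and 0.90^15 = 0.206, a difference of 0.478.

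| r | No event at all | Event but empty table, q = 10% | q = 25% | q = 50% |
|---|---|---|---|---|
| 5% | 46% | 46% | 37% | 22% |
| 10% | 21% | 65% | 48% | 26% |
| 20% | 3.5% | 70% | 43% | 17% |

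The column for no event at all is also the chance of an empty table if every such event were recorded (q = 1). The other columns are not error rates: where an event truly is unrelated, leaving it out of a device-related count is correct. They show how often an empty table would coexist with at least one event.

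**The case against.** The strongest reply is that this is a choice openly made. The device is marketed and used within its labelling, the study is small and descriptive, its objective is efficacy, and the endpoint is labelled as device-related, so the report would not misstate what it counts. That stands, and it limits the seriousness of the point. It does not supply the missing counts.

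Several stronger readings are tempting, and the documents do not support them.

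- **That events judged unrelated leave no trace and can never be reviewed.** They may show in the oxygen data, treatment log, collected exceptions, exit form and planned data listings. Section 6.2 also provides for access to source documents. The gap is that no safety analysis uses these sources.
- **That the unblinded site is the stated judge of relatedness.** No assessor is named. The inference is reasonable, because reports start at the site and the sponsor reviews what it receives, but it remains an inference.
- **That nothing prompts collection because Table 1 has no row.** The event-driven duties in 5.2 and 6.1 run without a visit row, and the CRFs are not among the documents. Those duties are still directed at device effects, complaints and alleged injuries.
- **That patients expected to need ventilation will be enrolled.** The exclusion wording leaves room for this when atelectasis is the cause, but no section says so. The phrase about rising support needs is narrative in 3.2, not a criterion in 3.2.1. The text supports a population at risk, no more.
- **That the first treatment session falls outside the recording window.** The synopsis wording can be read that way, but it can equally mean from the start of therapy, and 5.2 covers the whole study. This needs only aligned wording.

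It is also true that, without a comparator, an all-cause count would not establish device harm. Its use is to let a reader see and question the attribution.

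**Conclusion.** The concern holds in a limited form. Safety recording, serious-event reporting and tabulation are confined to events judged device-related, with no assessor or criteria given. Serious respiratory events judged unrelated would therefore be absent from the safety table and visible, if at all, only through data with no stated safety analysis. This rests on the text and needs no assumption.

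The size cannot be derived from the documents. Over the assumed ranges (r from 5% to 20%, q from 10% to 50%), the chance of at least one event together with an empty table runs from 17% to 70%. The plan should be changed on this point. The primary endpoint analysis is unaffected.

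**What to change.** Amend the synopsis Methods, 3.3 Safety, 3.5.2 Safety and Table 1, and carry the same wording into the synopsis entries for endpoints and statistical methods.

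1. Record all serious and all respiratory adverse events whatever the cause, from the start of the first session through Day 4 or discharge. Make relatedness a recorded field, with a named assessor and stated criteria.
2. Tabulate all-cause and device-related events side by side, with all treated subjects as the denominator. Include counts of mechanical ventilation, new pneumothorax and death.
3. Take pneumothorax from the existing routine radiology reports. With four films per subject this is at most 15 × 4 = 60 reports, with no new film or reader.
4. Add an adverse-event row to Table 1.
5. Align the synopsis recording window with 5.2.

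The cost is a protocol amendment, one CRF page and brief chart abstraction for about 15 inpatients through Day 4. More events will be listed that prove unrelated. The 24-hour reporting duty in 5.2 can stay as it is.
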